## **5. PARTICIPANT SELECTION AND ENROLMENT**

### **5.1 IDENTIFYING PARTICIPANTS**

There will be no trial specific screening tests performed. The patient will receive routine acute clinical assessment including severity of illness assessment (vital signs and blood lactate measurement - which is needed to complete the randomisation) and be treated in accordance to current UK guidelines (Sepsis 6) [2,37]. The results of these will inform trial eligibility and the patient may be approached as soon as these are available. Patients may be approached up to 12 hours after presentation if their clinical condition means that fluid resuscitation needs to commence. This time window has been chosen as it allows the longest reasonable period for recruitment from arrival where the patient could be deemed to be receiving acute assessment.

Patient and clinician will be unaware of treatment allocation until after randomisation. The research team, where it is locally agreed that they are part of the clinical care team, will identify patients using triage information and clinical or electronic records in the Emergency Department, Medical or Surgical Assessment Units or any other area used for acute assessment in the recruiting site. In this case, it is anticipated they would identify patients and make the first approach. Any member of the clinical team who has received general and trial specific training and is on the delegation log may also identify patients in this way.

Where researchers are not considered to be part of the care team, the researcher should ask a member of the direct care team to identify suitable patients and ask permission from the patient to be approached by the researcher to discuss participation.

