### **5.5 RANDOMISATION**

#### **5.5.1 Randomisation Procedures**

After assessment for eligibility and consent, the researcher or a delegated member of the clinical team will collect the baseline data necessary to complete the pre-randomisation information on the eCRF (a blood lactate measurement is required in order to complete the randomisation). Vital signs and blood lactate taken within the last hour can be used to make the assessment. Use of clinical care results taken prior to consent is permitted. If greater than one hour ago, a further blood lactate should be measured prior to randomisation. Randomisation will be carried out using a web-based randomisation service (managed by the Edinburgh Clinical Trials Unit (ECTU)) that ensures allocation concealment. Randomisation will be carried out within 12 hours of arrival at the hospital and within one hour of the decision being made that fluid resuscitation should be commenced. Once a patient is randomised, they will remain in the study and have all outcomes recorded regardless of compliance with randomised pathway allocation, unless they specifically withdraw consent to have data stored. Consented patients will be randomised on a 1:1 basis to albumin or balanced crystalloid in addition to standard care and will be stratified by age (<70 and ≥70) and lactate (<2 and ≥2) and study site.

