## 4.2 Baseline data

A table showing baseline demographic and clinical characteristics overall and by allocated intervention will include:

- a) Age (at randomisation in years)
- b) Sex (Male / Female)
- c) NEWS Score including individual components (1. Respiratory rate, 2. Oxygen saturations, 3. Temperature, 4. Systolic blood pressure, 5. Heart rate, 6. Glasgow Coma Scale (GCS))
- d) Lactate (mmol/l)
- e) Vital signs (pulse (bpm), systolic and diastolic blood pressure (mmHg), fraction of inspired oxygen (FiO2) (%))
- f) Routine blood results (glucose (mmol/L), eGFR (mL/min/1.73m^2), albumin (g/l), ALT (U/L or iU/L), troponin (ng/l), urea (mmol/L), creatinine (μmol/L), WCC (x10^9/L), Hb (g/l), platelets (x10^9/L), neutrophils (x10^9/L), CRP (mg/l), procalcitonin (ug/L or ng/mL)).
- g) Expected source of infection (chest, urine, CNS, skin, abdomen, missing, unknown, other)
- h) Co-morbidities (cancer, stroke, MI, peripheral vascular disease, heart failure, cardiac obstructive pulmonary disease, chronic kidney disease, diabetes type I/ II & dementia)
- i) Average volume of fluid (mL) given prior to randomisation.

No formal statistical testing of the baseline characteristics will be performed. The first relevant observation will be presented if more than one observation was collected.

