#### **4.4 Primary outcome**

1) This will be the proportion of those screened who were randomised (number randomised/ number screened) with a 95% CI.

2) The main clinical outcome is 30-day mortality, under intravenous 5% Human Albumin compared with intravenous balanced crystalloid in the early resuscitation phase of management of adults with community acquired sepsis.

A mixed effects logistic regression model will be used, including a fixed effect for intervention group adjusted for site (as a random effect) and baseline covariates known to be strong predictors of 30-day mortality (age; active cancer; heart failure). The intervention effect will be reported as an odds ratio and 95% confidence interval. The assumptions for mixed effects logistic regression will be assessed to ensure compliance. If this model proves inappropriate, a suitable alternative will be used.

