#### **4.5 Subgroup analyses**

The following subgroup analyses will also be considered based on a 30 day mortality outcome, provided there are sufficient outcomes per subgroup:

- 1) Severity of illness at recruitment 1. NEWS/NEWS2 (5-6, 7+)
- 2) Severity of illness at recruitment 2. qSOFA ( $\leq 1$ ,  $> 1$ )
- 3) Severity of illness at recruitment 3. lactate ( $\leq 2$ mmol/L,  $> 2$ mmol/L)
- 4) Age ( $< 70$ ,  $\geq 70$  years)
- 5) Pre-existing known heart failure (Y/N)
- 6) Pre-existent chronic kidney disease (Y/N)
- 7) Admission to a critical care bed (HDU or ICU) (Y/N).

These will initially be assessed by reviewing the number of outcomes per subgroup per site.

Where feasible, for each of the subgroup analysis listed above the effect of entering the treatment by subgroup interaction into the mixed effects logistic regression model will be examined. If necessary, sites will be grouped according to region and/or size. The odds ratio, plus 95% confidence interval, will be presented for the interaction. Within subgroup treatment effect odds ratios and confidence intervals will also be presented. No other baseline

covariates will be included in these analyses. If feasible, these results will be presented as a Forest plot.

Subgroup analysis findings should be interpreted with caution due to the small number of outcomes anticipated per subgroup and the number of subgroup analyses.

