- a) If the data permits, the effect of compliance (what cumulative dose of novel intervention or standard care was received) on intervention effect will be explored using a complier average causal effects approach. Descriptive analysis of changes in compliance over time in small and large sites may also be considered.
- b) Other continuous outcomes (e.g. volume of intravenous fluid, length of stay) will be analysed using mixed effects linear models, while the other outcomes involving proportions (e.g. proportion receiving renal replacement therapy, vasopressor infusion, invasive ventilation, readmissions within 90 days) will be analysed as per the main clinical outcome (with a mixed effects logistic regression). Site will be included as the random effect.
- c) The intervention effect on proportion admitted to critical care (HDU or ICU) will be analysed using mixed effects logistic regression as per the main clinical outcome.
- d) The observed patterns of any missing data will be reported by randomised group, across the range of outcomes measured and, where appropriate, by time of measurement. This will inform the missing data handling strategies to be taken forward in the subsequent confirmatory trial.

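### The SAP 4.4 mortality model leaves out the lactate stratum used to randomise; adding it is a small improvement that needs no new data

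*SAP*

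**What the plan says.** Protocol 5.5.1 allocates 1:1, and allocation "will be stratified by age (<70 and ≥70) and lactate (<2 and ≥2) and study site". A lactate value is a condition of entry: "a blood lactate measurement is required in order to complete the randomisation". An old value has to be replaced: "If greater than one hour ago, a further blood lactate should be measured prior to randomisation".

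SAP 4.4 fits a mixed effects logistic regression for 30-day mortality, with a fixed treatment effect, site as a random effect, and "baseline covariates known to be strong predictors of 30-day mortality (age; active cancer; heart failure". It does not mention lactate, and it does not say whether age enters as a continuous variable or as the two strata.

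Both documents class lactate as severity of illness. Protocol 5.1 refers to "severity of illness assessment (vital signs and blood lactate measurement - which is needed to complete the randomisation", and SAP 4.5 lists "Severity of illness at recruitment 3. lactate" as a subgroup factor, split at 2 or below versus above 2. SAP 4.2 tabulates lactate at baseline under the rule "The first relevant observation will be presented if more than one observation was collected".

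**The concern.** When a trial balances its arms on a factor and that factor predicts the outcome, a model that ignores the factor takes no account of the balance. The test then tends to be a little conservative and some power is lost. In a logistic model the treatment odds ratio is also closer to 1 than it would be conditional on the factor.

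Here the design treats lactate as important enough that nobody can be randomised without it, yet the main clinical model drops it while keeping the other two strata. Protocol 10.2 uses the interval around the mortality difference to plan the definitive trial, so the treatment estimate is a working output even though all tests are informal (SAP 3).

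**Working it through.** **1. The plan's own power figure.** Protocol 10.1 gives 90% power for 35% versus 18% with 300 randomised. With 150 per arm, two-sided 5%:

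- pooled rate (0.35 + 0.18)/2 = 0.265; null SE = √(2 × 0.265 × 0.735/150) = 0.0510
- SE under the alternative = √[(0.35 × 0.65 + 0.18 × 0.82)/150] = 0.0500
- z = (0.17 − 1.96 × 0.0510)/0.0500 = 1.40, so power is 92.0%

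The size for 90% is 140 per arm, or 152 per arm (304 in total) with continuity correction. The stated figure reproduces to within 2 points.

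**2. Strata against model terms.**

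| Randomisation stratum (Protocol 5.5.1) | Term in SAP 4.4 |
|---|---|
| Site | Yes, random effect |
| Age, <70 / ≥70 | Yes, form not stated |
| Lactate, <2 / ≥2 | No |

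Protocol 10.2 asks for site plus prespecified strong predictors of death. It does not promise adjustment for every stratum.

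**3. Size of the effect.** The models compared are

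logit P(death) = α + β·treatment + γ₁·age + γ₂·cancer + γ₃·heart failure (+ δ·lactate stratum) + site.

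From the documents: N = 300, 1:1 allocation, about 15 sites, and 35% versus 18% (Protocol 10.1). A lower scenario, 20% versus 10%, takes the index-hospitalisation mortality of around 20% in Protocol 1.1 as if it were 30-day mortality and applies the same halving.

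Assumed, because the documents do not say:

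- lactate–death odds ratio 1 to 4, and half of patients at lactate ≥2
- continuous age with mean 70 (Protocol 1.1) and SD 15, giving an odds ratio of about 2 between the age strata
- cancer in 15% (odds ratio 1.8) and heart failure in 12% (odds ratio 1.6)
- site SD 0.3 on the log-odds scale
- permuted blocks of 4 within site × age × lactate

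The main simulation ran 20,000 trials per scenario and fitted the random site intercept. The gain in power from adding lactate was:

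| Assumed lactate odds ratio | 20% vs 10% (from about 69.5%) | 35% vs 18% (from about 93.3%) |
|---|---|---|
| 1.5 | +0.4 points | 0.0 |
| 2 | +0.8 | +0.4 |
| 3 | +1.5 | +0.7 |
| 4 | +2.0 | +1.1 |

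- If lactate has no effect (odds ratio 1), power changes by −0.01 to +0.12 points.
- Type I error is 3.9% to 5.2% without lactate and 4.7% to 5.3% with it.
- Without lactate the treatment log-odds ratio is 1.0% to 2.6% nearer zero at lactate odds ratios of 1.5 to 2, and 4.1% to 8.4% nearer at 3 to 4.
- Adding lactate moves the SE of the log-odds ratio (no treatment effect, 20% mortality) from 0.303 to 0.304 at odds ratio 1.5, and from 0.302 to 0.314 at odds ratio 4.
- The SE of a mortality difference standardised from the model falls by 0.4% (odds ratio 1.5) to 5.0% (odds ratio 4).

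A second simulation used 3,000 trials per scenario, slightly different covariate assumptions and no site term in the fit. Its power gains at lactate odds ratios 1, 1.5, 2, 3 and 4 were 0.0, 0.2, 0.3, 0.6 and 1.3 points at 35% versus 18%, and −0.2, −0.2, 0.4, 1.0 and 2.7 points at 20% versus 10%. At odds ratio 4 and 35% versus 18%, the mean treatment odds ratio was 0.378 without lactate and 0.346 with it, against a true conditional value of 0.349. On the log scale that is 1 − ln(0.378)/ln(0.346) = 8.3% nearer zero.

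A third run, also without a site term in the fit, gave gains of about 0.8 to 2.5 points at odds ratio 4 and about 0.5 at odds ratio 2, with type I error moving from 4.2% to 4.8% at odds ratio 4.

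**4. Room for one more term.** Expected deaths are 150 × 0.35 + 150 × 0.18 = 79.5, or 150 × 0.20 + 150 × 0.10 = 45. With five fixed-effect terms (treatment, age, cancer, heart failure, lactate) that is about 16 or 9 deaths per term.

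**5. The cut.** The stratum is <2 / ≥2 and the SAP 4.5 subgroup is ≤2 / >2. They differ only for a value of exactly 2.0, and the number of such patients is unknown. The age subgroup does match its stratum.

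**The case against.** The analyses are exploratory and the tests informal, so a point or two of power decides nothing. SAP 4.4 follows the covariate rule of Protocol 10.2, and neither document says that lactate predicts death. At assumed odds ratios of 1 to 2 the gain is under 1 point. On the log-odds scale that SAP 4.4 reports, adding the term widens the interval. Lactate is already balanced by design, tabulated by arm and examined as a subgroup. Changing the main clinical model of an open-label trial after recruitment has its own cost.

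Most of this stands as an argument about weight. The interval for the mortality difference narrows only if that difference is derived from the model, which SAP 4.4 does not specify. It does not remove the point. A baseline table and a subgroup interaction do not adjust the main estimate, and SAP 4.5 leaves the other baseline covariates out of the subgroup models. The added term is fixed by the design rather than chosen from the data, so a dated change made before the comparison leaves little room for selection.

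A reader might infer three stronger things that the documents do not support:

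- **That the SAP breaches the protocol.** Protocol 10.2 requires site and strong predictors, not every stratum.
- **That the estimate is biased or the test invalid.** The error runs to the conservative side, and the odds ratios with and without lactate are different estimands.
- **That secondary outcomes need a new event-count rule.** SAP 4.6 applies the same model to outcomes such as "proportion receiving renal replacement therapy, vasopressor infusion, invasive ventilation, readmissions within 90 days", where events may be few and an extra term may fit poorly. Their counts are not known, and SAP 4.6 already allows another method where the data do not support the planned one.

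**Conclusion.** The point holds, at low weight. Lactate is the only stratification factor missing from the SAP 4.4 model, and the omission is unexplained. If lactate predicts death, the model as written is slightly conservative (type I error about 4% to 5%), loses about 0 to 2.5 points of power, and reports a treatment log-odds ratio about 1% to 8% nearer zero than the lactate-conditional one. If lactate has no effect, adding it costs essentially nothing.

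These sizes rest on the assumed lactate odds ratio of 1 to 4, the assumed prevalence, covariate effects and block scheme, and age entered as continuous. The upper end needs a strong lactate effect and the lower mortality scenario.

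**What to change.** - **SAP 4.4:** add the lactate stratum (<2 versus ≥2) as a fixed effect beside age, active cancer, heart failure and the random site effect. Use the value entered at randomisation. The first recorded value, shown in the SAP 4.2 table, can differ from it when the lactate was repeated.
- **Timing:** record the change and its reason, dated before the treatment comparison is run. The SAP abstract describes recruitment in the past tense, and the trial is open label.
- **SAP 4.5:** set the lactate subgroup to <2 versus ≥2.
- **SAP 4.6:** add no new rule. Where a secondary binary outcome has too few events for the model, use the existing provision for alternatives.

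The cost is a documented SAP change, one extra parameter with about 45 to 80 expected deaths, and a slightly larger standard error on the log-odds scale. No new data are needed, because the lactate value is already required to randomise.

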#### **4.5 Subgroup analyses**

The following subgroup analyses will also be considered based on a 30 day mortality outcome, provided there are sufficient outcomes per subgroup:

- 1) Severity of illness at recruitment 1. NEWS/NEWS2 (5-6, 7+)
- 2) Severity of illness at recruitment 2. qSOFA ( $\leq 1$ ,  $> 1$ )
- 3) Severity of illness at recruitment 3. lactate ( $\leq 2$ mmol/L,  $> 2$ mmol/L)
- 4) Age ( $< 70$ ,  $\geq 70$  years)
- 5) Pre-existing known heart failure (Y/N)
- 6) Pre-existent chronic kidney disease (Y/N)
- 7) Admission to a critical care bed (HDU or ICU) (Y/N).

These will initially be assessed by reviewing the number of outcomes per subgroup per site.

Where feasible, for each of the subgroup analysis listed above the effect of entering the treatment by subgroup interaction into the mixed effects logistic regression model will be examined. If necessary, sites will be grouped according to region and/or size. The odds ratio, plus 95% confidence interval, will be presented for the interaction. Within subgroup treatment effect odds ratios and confidence intervals will also be presented. No other baseline

covariates will be included in these analyses. If feasible, these results will be presented as a Forest plot.

Subgroup analysis findings should be interpreted with caution due to the small number of outcomes anticipated per subgroup and the number of subgroup analyses.

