## 10.2 PROPOSED ANALYSES

All statistical analyses will be governed by a comprehensive Statistical Analysis Plan authored by the study statistician and agreed by the independent Trial Steering Committee. As a feasibility pilot trial, all analyses will be exploratory and mainly descriptive. The primary outcome of recruitment feasibility will be assessed as the proportions who visited the ED that were (a) eligible, and then (b) of those who were eligible that were approached and then (c) of those eligible and approached the proportion that consented to be randomised. The clinical primary outcome of all causes mortality at 30 days will be summarised by randomised treatment group and then analysed using a mixed effects logistic regression adjusting for site and adjusting for pre-specified baseline covariates known to be strong predictors of 30-day mortality. The range of possible treatment effects indicated by the 95% confidence interval around the estimate of difference in 30-day mortality, and that around the 30-day mortality rate in the standard of care group will be used to inform the design of a definitive trial. We plan a number of important predefined exploratory sub-group analyses on the primary outcome including severity of illness at recruitment (NEWS/NEWS2, qSOFA, lactate), age, pre-existing known heart failure, pre-existent chronic kidney disease, baseline albumin. We will also undertake a subgroup analysis of primary outcome for all patients not admitted to a critical bed (HDU or ICU) If the data permits, we will consider additional analyses exploring compliance (what cumulative dose of novel intervention or standard care was received) using causal models with an instrumental variable approach. Secondary outcomes (e.g. volume of intravenous fluid, length of stay) will be analysed using mixed effects linear models, while the secondary outcomes involving proportions (e.g. proportion receiving renal replacement therapy, vasopressor infusion, invasive ventilation, readmissions within 90 days) will be analysed as per the primary outcome (with a mixed effects logistic regression). The proportions admitted to critical care (HDU or ICU) will be analysed using a proportional odds logistic regression. The safety outcomes will be analysed in a similar way according to their distribution. The quality of life data (at 180 days) will be analysed likewise with a model appropriate to the distribution. We will be interested in understanding the observed patterns of any missing data.

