#### 4.6 Other analyses

The following data will be summarised descriptively, by randomised group and overall:

A	B	C
	Objective	Endpoints to display
1	Assess mortality rate during index hospitalisation, in-hospital and at 90 days	a) In-hospital mortality (index admission) and b) 90-day mortality
2	Assess the ability to deliver the trial including the time to first dose, data completeness and participant withdrawal	Data completeness (%)
3	Assess the total volume of intravenous fluid in each arm at 6 hours and 24 hours	Volume of randomised fluid delivered in each arm a) in the first 6hrs and b) more than 6hrs to 24hrs
4	Assess the level of critical care interventions administered	Proportion of participants needing critical care intervention: a) Intravenous vasopressors, b) renal replacement therapy and c) invasive ventilation
5	Investigate the length of hospital stay including critical care (HDU/ICU) admission	a) Proportion of patients admitted to critical care (HDU/ICU) b) Length of stay in critical care (HDU/ICU) c) Length of hospital stay
6	Investigate the proportion of patients readmitted to hospital in first 90 days after discharge	Proportion of patients readmitted in first 90 days after discharge

A	B	C
7	Delineate the proportion of patients developing any complications including acute kidney injury, pulmonary oedema and allergy including severe allergic reactions	Proportion of patients developing each, or any, of: a) acute kidney injury (as defined by NICE https://cks.nice.org.uk/acute-kidney-injury#!scenario ); b) pulmonary oedema (radiology diagnosis or requirement for rescue management (new diuretic use)); and c) allergy or anaphylaxis (requirement for rescue management (antihistamines, adrenaline, intravenous fluids, steroids))
For the economist		
8	To assess patient quality of life measures using EQ-5D-5L questionnaire	Health Related Quality of life (EQ-5D-5L) for the first 50 patients randomised (see section 4.8) a) at baseline b) at 7 days and c) at 180 days
9	To assess secondary care costs at 30 days	Service use at 30 days: a) number of readmissions, and b) length of stay at ward level and in critical care (HDU/ICU)

In addition, the following exploratory analyses will be considered. If deemed inappropriate based on available data, where feasible, suitable alternatives will be used:

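### SAP 4.5 analyses critical-care admission, a post-randomisation outcome, alongside baseline subgroups without warning that its odds ratios may not be randomised comparisons; separately, it omits the protocol's baseline albumin subgroup without a reason

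*SAP*

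**What the plan says.** SAP 4.5 names seven subgroups for 30-day mortality. Six are characteristics at recruitment: NEWS/NEWS2, qSOFA, lactate, age, heart failure and chronic kidney disease. The seventh is "Admission to a critical care bed (HDU or ICU) (Y/N". All seven are handled alike. Counts come first: "These will initially be assessed by reviewing the number of outcomes per subgroup per site". Where feasible, a treatment-by-subgroup interaction is then fitted. "Within subgroup treatment effect odds ratios and confidence intervals will also be presented", if feasible in a forest plot. The only warning is: "Subgroup analysis findings should be interpreted with caution due to the small number of outcomes anticipated per subgroup and the number of subgroup analyses".

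Elsewhere admission is an outcome. It is secondary endpoint 8 in protocol 2.2.2. SAP 4.6 row 5 displays "a) Proportion of patients admitted to critical care (HDU/ICU" by arm, and SAP 4.6(c) models the effect of the intervention on it.

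The item originates in protocol 10.2, which plans a "subgroup analysis of primary outcome for all patients not admitted to a critical bed (HDU or ICU". That is one stratum only, in a sentence separate from the baseline factors. The SAP turns it into a yes/no interaction and adds it to the list.

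The baseline list in protocol 10.2 ends with "pre-existent chronic kidney disease, baseline albumin", and SAP section 2 reproduces that text. Albumin is collected (protocol 8.1) and tabulated at baseline (SAP 4.2: "albumin (g/l), ALT (U/L or iU/L"). SAP 4.5 does not list it and gives no reason.

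**The concern.** Randomisation makes the arms comparable within groups defined before treatment. It does not do so within groups defined by something that treatment may alter. Trial fluid is given in the first six hours after randomisation (protocol 3), and treating clinicians know the allocation (protocol 5.5.3), so the fluid or knowledge of it could change who goes to HDU or ICU. If so, admitted patients in one arm differ in underlying severity from admitted patients in the other, and the same holds for patients who stay on the ward.

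The stake is a contrast that may not be causal being read as a randomised subgroup effect. The not-admitted stratum matters most. It holds most of the deaths, and it is the ward-managed population on which the trial's rationale rests (protocol 1.1). A definitive trial that copied the list would inherit the problem, and a larger sample would not remove it.

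For albumin, a subgroup that the protocol promised goes unreported and the reader cannot tell why.

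**Working it through.** The plan gives no figure for this analysis, so the check is a model in which treatment affects admission but never death.

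**Inputs from the documents.** 300 randomised 1:1, so 150 per arm (protocol 4.1, 5.5.1). Mortality of 20% (protocol 1.1, index stay) or 35% (protocol 10.1, standard of care). Admission of 5-10% (protocol 1.1). About 15 sites.

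**Assumed inputs.** Severity X is standard normal. Logit P(death) = a + 1.0·X in both arms. Logit P(admission) = b + s·X, with s equal to 1.0 or 1.5 and allowed to differ by arm. Intercepts are solved to give the stated overall rates. A further case of 30% v 20% admitted lies above the protocol's range.

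**Formulas.** Expected deaths among admitted patients in an arm = 150 × E[P(admission|X) × P(death|X)], by 200-point Gauss-Hermite integration. The odds ratio (OR, HAS over control) comes from the expected counts. SE(log OR) = √(sum of 1/count). Bias in standard errors = ln(OR)/SE. Interaction = ratio of the two stratum odds ratios.

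**Worked case: 20% mortality, 10% admitted in control and 5% in HAS, s = 1.5 in both.**
- Admitted: control 15 patients, 5.75 deaths, 9.25 survivors; HAS 7.5 patients, 3.09 deaths, 4.41 survivors. OR = (3.09/4.41)/(5.75/9.25) = 1.13. SE = √(1/3.09 + 1/4.41 + 1/5.75 + 1/9.25) = 0.912. Bias = ln(1.13)/0.912 = 0.13. The 95% CI multiplies and divides the odds ratio by exp(1.96 × 0.912) = 6.0.
- Not admitted: control 24.25 deaths, 110.75 survivors; HAS 26.91 deaths, 115.59 survivors. OR = 1.06. SE = 0.310. Bias = 0.20. CI factor 1.8.
- Interaction = 1.130/1.063 = 1.06.

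**Odds ratios when the truth is 1, at 20% mortality (bias in SE in brackets):**

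| Admitted, control v HAS | s, control / HAS | Admitted | Not admitted | Interaction |
|---|---|---|---|---|
| 10% v 10% | 1.5 / 1.5 | 1.00 | 1.00 | 1.00 |
| 10% v 8% | 1.5 / 1.5 | 1.04 (0.06) | 1.02 (0.08) | 1.02 |
| 10% v 5% | 1.5 / 1.5 | 1.13 (0.13) | 1.06 (0.20) | 1.06 |
| 10% v 10% | 1.5 / 1.0 | 0.80 (-0.30) | 1.04 (0.12) | 0.77 |
| 10% v 10% | 1.0 / 1.5 | 1.25 (0.30) | 0.96 (-0.12) | 1.30 |
| 10% v 5% | 1.5 / 1.0 | 0.85 (-0.17) | 1.09 (0.27) | 0.79 |
| 10% v 5% | 1.0 / 1.5 | 1.42 (0.38) | 1.02 (0.07) | 1.39 |
| 30% v 20% | 1.5 / 1.5 | 1.14 (0.26) | 1.11 (0.28) | 1.03 |
| 30% v 20% | 1.5 / 1.0 | 0.96 (-0.08) | 1.18 (0.46) | 0.81 |
| 30% v 20% | 1.0 / 1.5 | 1.30 (0.51) | 1.01 (0.03) | 1.28 |

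At 35% mortality, the 10% v 5% case with s = 1.0 / 1.5 gives 1.43 (0.39) among the admitted. The 30% v 20% cases reach 0.51 SE (not admitted) and 0.58 SE (admitted). Swapping the arms inverts every odds ratio, for example 1/1.42 = 0.70.

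A simpler check with two severity classes, in which 7.6% to 18.5% of control patients are admitted, also gives 1.00 in both strata when admission is unaffected. It gives 0.71 to 1.27 (admitted) and 0.99 to 1.22 (not admitted) when treatment reduces admission in one class by a quarter or a half.

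**Counts against the feasibility check.** At 20% mortality with equal admission, deaths among the admitted total 11.5 (10% admitted) or 6.2 (5%), that is 11.5/15 = 0.77 or 6.2/15 = 0.41 per site. Deaths among the not admitted total 48.5 or 53.8.

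**Albumin sample timing.** Protocol 5.5.1 ties only vital signs and lactate to a window before randomisation. Protocol 7.1 records routine bloods daily within 12 hours either side, and SAP 4.2 takes the first relevant observation. Nothing shows that the baseline albumin sample precedes HAS.

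**The case against.** The analysis is a protocol commitment and serves the trial's main population. Everything is exploratory, tests are informal and read descriptively (SAP 3), the subgroups are only to be considered, and the feasibility check may stop item 7. This limits the consequence, but none of it tells a reader that the strata may be non-comparable. The feasibility check looks at outcome counts, not at whether treatment affects the grouping. Nor can it be relied on to stop item 7: SAP 4.5 allows sites to be grouped, so deaths per site are not the effective threshold, and the not-admitted stratum has ample deaths.

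It is fair that SAP 4.5 never heads its list as baseline. That reading rests on items 1 to 6 and on the SAP's remark that no other baseline covariates will enter the models. It is also fair that deleting the not-admitted analysis would go further than the harm requires; labelling and separation are enough.

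Three stronger readings are not supported:
- A reader might infer that the odds ratios will be biased. That requires treatment to affect admission, which the documents leave open.
- A reader might take the table's largest value as a ceiling. It is only the largest of the cases tried. Nor do equal admission rates rule bias out, as the two equal-rate rows with different slopes show.
- A reader might suspect that albumin was dropped because of the data. The documents give no reason at all, so they do not support that inference.

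**Conclusion.** The point holds as a gap in labelling and placement, worth considering and minor in this trial. The textual facts are certain: the grouping variable is a post-randomisation outcome in the plan's own terms, and the caution does not address that.

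The size is conditional. With no effect on death and the assumed severity slopes, the bias reaches about 0.4 standard errors at 5-10% admitted and about 0.6 at 20-30%, in either direction. It is zero if admission is unaffected. Sampling error dominates throughout: in the worked case the 95% CI factors are 6.0 and 1.8. No primary analysis, sample size or power figure is touched.

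The albumin omission is a separate, plain discrepancy between protocol and SAP that needs no modelling. Because the sample is not shown to precede treatment, restoring it without a timing condition could repeat the same fault.

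**What to change.** 1. Take item 7 out of the baseline subgroup list and forest plot. Report 30-day mortality by arm and admission status separately, beside the admission rate by arm already planned in SAP 4.6. Label it as conditioned on a post-randomisation outcome and not a randomised subgroup effect.
2. If a modelled not-admitted estimate is kept to honour protocol 10.2, give it the same label. If it is dropped, record the departure.
3. Extend the SAP 4.5 caution to say this. The label limits misreading but does not remove selection. The NEWS, qSOFA and lactate subgroups describe baseline severity and do not replace a ward-managed group.
4. Restore baseline albumin as a continuous interaction or with a cut-off fixed before analysis, using only samples taken before trial fluid started and giving the number missing by arm. Otherwise state why it was dropped.

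The cost is SAP wording, a less prominent ward-managed estimate, and some patients without a pre-treatment albumin, since protocol 7.1 does not require bloods that the clinical team did not request.
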